#### c) Baseline demographics

- a. Pre-transplant comorbidity index (Sorror)
- b. Underlying disease requiring transplantation
- c. Disease stage at the time of transplant
- d. Donor type
- e. Graft Source
- d) GVHD-associated measurements at baseline and after initiation of corticosteroids at Day 14(+/-5), 28 (+/-5), and 56 (+/-5)
  - a. Organ Stage and Grade of GVHD (see Table 1)
  - b. Corticosteroid dose at that time and cumulative corticosteroid dose through day 56.
    - Doses of methylprednisolone will be converted to prednisone equivalents by multiplying the methylprednisolone dose by 1.25. Prednisone doses for each subject will be converted to mg/kg. The cumulative and average corticosteroid doses will be calculated over time.
  - c. GVHD Response (at days 14, 28, 56)
  - d. Body mass index (BMI), albumin, prealbumin levels. Albumin and possibly prealbumin levels are collected by the stem cell transplant team whether

the patient is on study or not (standard of care) and are not researchspecific procedures. Prealbumin levels will be recorded if they are obtained by the medical team.

- e) During the Day 180 post-transplant follow up:
  - a. Acute and chronic GVHD assessment, if patient is returning to MDACC
    - i. Grade of GVHD, GVHD response
  - b. Body mass index (BMI), albumin levels, will be collected from the medical record if available.
  - c. Non-Relapse Mortality: non-relapse mortality due to any cause other than the underlying malignancy, will be assessed at Day 180
  - d. Overall survival: Overall survival will be computed up to Day 180

With the exception of the baseline demographic information, physical/functional measures, patient reported questionnaires, and GVHD-associated measurements will be recorded at the following time points:

- a. Baseline (at the time of screening, consent and enrollment into the study)
- b. Day 14 (+/-5)
- c. Day 28 (+/-5)
- d. Day 56 (+/-5)

It will take approximately 15 minutes to perform the physical function tests and it will take approximately 20 minutes to complete the patient questionnaires during each patient evaluation session.

If a participant remains hospitalized as an inpatient, he or she will continue to participate in the exercise program allocated to them and the above measures will be recorded at the appropriate time intervals. The medical indication for hospitalization, discharge diagnoses and length of hospital stay will be recorded.

#### Table 1: Overall Acute GVHD Response

Participants will be graded according to the modified Keystone Grading Schema displayed in the table below.

|                      | Stage 0                     | Stage 1   | Stage 2                                 | Stage 3                          | Stage 4  |
|----------------------|-----------------------------|---|---|----------------------------------|--|
| Skin                 | No Rash                     | Rash <25%
BSA                                    | 25-50%
BSA                           | >50%
BSA                      | Bullae and desquamation  |
| Lower
GI
Tract | <500 ml/day
stool volume | 500-
1000 ml/day
stool volume
OR
Severe | 1001-
1500 ml/day
stool
volume | >1500 ml/
day stool
volume | Severe
abdominal
pain +/- ileus,
frank blood or
melena |

#### Modified Keystone Grading Schema

|         |                       | vomiting    |             |                  |           |
|---------|-----------------------|-------------|-------------|------------------|-----------|
| Liver I | Bilirubin
≤2 mg/dl | 2.1-3 mg/dl | 3.1-6 mg/dl | 6.1-
15 mg/dl | >15 mg/dl |

Abbreviations: BSA = body surface area; GI = gastrointestinal (1)

- 1. Acute GI GVHD Response Criteria: Proportion of subjects with CR, PR, MR, NR and Progression will be determined over time. Scoring of CR, PR, MR, Progression and NR will be in comparison to the participant's acute GI GVHD Stage (see lower GI tract row of above table). Response will be based on the following response definitions:
  - **Complete Response (CR)**: a Stage of 0 for the GVHD grading in the lower GI tract with no additional intervening therapy for their GVHD.
  - **Partial Response (PR)**: improvement by at least 1 Stage in GI GVHD symptoms without progression in others with no additional intervening therapy for their GVHD.
  - **Mixed Response (MR)**: improvement in lower GI tract with deterioration in another organ manifesting symptoms of GVHD or development of symptoms of GVHD in a new organ.
  - **Progression:** deterioration in lower GI tract.
  - No Response (NR): absence of any improvement or progression as defined above. Subjects receiving secondary therapy (including need to re-escalate steroid dose to ≥2.5 mg/kg/day of prednisone; or methylprednisolone equivalent of 2 mg/kg/day) will be classified as non-responders.
- 2. Response for All Organs Involved with Acute GVHD: Proportion of subjects with CR, PR, MR, Progression and NR for all organs involved with acute GVHD will be determined over time. Scoring of CR, PR, MR, Progression and NR will be in comparison to the participant's acute GVHD Stage (see table of Modified Keystone Grading Schema above). Response will be based on the following response definitions:
  - **Complete Response (CR)**: a Stage of 0 for the GVHD grading in all evaluable organs with no additional intervening therapy for their GVHD.
  - **Partial response (PR)**: improvement by at least 1 Stage in 1 or more organs involved with GVHD symptoms without progression in others with no additional intervening therapy.
  - **Mixed response (MR)**: improvement in 1 or more organs with deterioration in another organ manifesting symptoms of GVHD or development of symptoms of GVHD in a new organ.
  - **Progression:** deterioration in at least 1 organ without any improvement in others.
  - No response (NR): absence of any improvement or progression as defined. Subjects receiving secondary therapy (including need to re-escalate corticosteroid dose to ≥2.5 mg/kg/day of prednisone [or methylprednisolone equivalent of 2 mg/kg/day]) will be classified as non-responders.

#### **Patient Recruitment**

Eligible patients with newly diagnosed GVHD will be recruited from the MDACC outpatient stem cell transplant clinic and the MDACC inpatient stem cell transplant primary service. The stem cell transplant attending physician will be the primary recruiter to the study. Patients will be referred to our research team within 5 days of initiating corticosteroids for the presumptive diagnosis of GVHD. In the event that a patient's biopsy results in no GVHD, but the patient has been on high-dose corticosteroids for four or more days, they will still remain on study as they may still be at risk for steroid myopathy. The following screening tests will be performed after receiving verbal consent from the patient. Patients will complete the Physical Activity Readiness Questionnaire (PAR-Q). Furthermore, they will undergo baseline physical

functioning tests (walk 10 meters, 5x sit-to-stand test). Thus, their potential to participate in a home-based exercise program will be screened based on subjective reports and objective demonstration. Based on their responses, they will be enrolled onto the study or they will be triaged to the study principal investigators for further review. For instance, if they are having on-going cardiopulmonary symptoms, they will be re-evaluated by their primary stem cell physician for medical clearance for an exercise regimen and if they have musculoskeletal concerns, they will be referred to physical medicine and rehabilitation for further evaluation.

For the PAR-Q screening questions:

- If the patient has any "Yes" responses to questions 1-4, they will be referred back to the Stem Cell Transplant attending physician, who will decide to clear the patient for exercise, or if they require a cardiology consultation prior to initiating exercise.
- If they respond "Yes" to questions 5 and 7, they will be triaged to one of the Physical Medicine and Rehabilitation faculty who is over-seeing the study. They can potentially evaluate the patient face-to-face during the screening period, or will speak with the patient to determine their eligibility to participate in the study.
- In the event that the patient is excluded from the study based on the PAR-Q, the
  patient will either be referred to Physical Medicine and Rehabilitation for a clinical
  consultation to address their impairments or referred to outpatient physical and
  occupational therapy (where they may receive a supervised therapy program).

Participants from both inpatient and outpatient who are recruited for this study will receive a strengthening and walking program.

We plan to approach approximately 70 patients to invite them to participate in this study with an accrual of 3 new participants per month with an anticipated accrual period of approximately 24 months.

When the stem cell transplant team initiates a patient on corticosteroids for newlydiagnosed GVHD, they will contact our study staff. Our study staff will meet with the patient face-to-face at the stem cell transplant clinic or the Ambulatory Transfusion Clinic (ATC). Follow up visits will also be conducted in the stem cell transplant clinic or ATC, as this is where the patients will attend their routinely scheduled clinic appointments. They will be asked a series of questions about their exercise tolerance and to screen for any adverse events (script included). During the follow up face-toface visits (Day 14, 28, 56, and 180), we will obtain repeat measures (questionnaires and functional measures).

#### Exercise Regimen

The American College of Sports Medicine exercise guidelines for cancer survivors encourage a combination of 150 minutes of moderate-intensity aerobic activity and two to three weekly sessions of strength training, but caution that exercise programs should be adapted to the needs of each cancer survivor [21]. There are currently no guidelines for exercise in patients undergoing treatment for cancer. Studies show that exercise prior to and immediately after HSCT show significant differences strength, endurance, functional performance, and quality of life. [22, 23]. There is also evidence that isokinetic strength training can reverse corticosteroid-induced muscle wasting [24]. As muscle weakness and deconditioning are frequently seen sequelae after HSCT and as steroid myopathy develops, patients are often referred to physical and occupational therapy to address the weakness. Thus, it is important to employ an exercise and endurance regimen to preserve strength and to circumvent further functional decline.

# The exercise regimen will include an 8-week, home-based strengthening walking program.

- MDACC physical medicine and rehabilitation (PM&R) physicians will supervise the conduct of the exercise intervention.
- Research staff trained by the PM&R faculty will implement the exercise intervention.
- Furthermore, many of these patients receive outpatient physical therapy as standard of care. If the participant is receiving outpatient physical therapy, the skilled therapy team will incorporate this exercise regimen in their outpatient program and the participant will be encouraged to continue with our exercise regimen as their home program.
- The inpatient and outpatient groups will be given the same set of exercises (strengthening and walking), instructions for adherence, and follow up measurements will be conducted at the standard time intervals as outlined in in Section V:
  - Baseline (at the time of screening, consent and enrollment into the study)
  - Day 14 (+/-5)
  - Day 28 (+/-5)
  - Day 56 (+/-5)
  - Day 180 post transplant (+/- 30 days)

# a) Resistance/strengthening

All participants will be instructed to perform resistance/strengthening exercises for a 30 minutes period three times a week. The resistance exercises used in this study are designed to engage multiple upper body muscles and lower limb muscles.

The exercises consist of seated and standing weight-bearing exercises. The patients will start with body-weight based exercises and will graduate to ones requiring resistance with the use of exercise bands. The upper body exercises will strength deltoids, scapular stabilizers, triceps and rotator cuff musculature. These exercises will include the use of elastic exercise bands. The lower limb

exercises will strengthen the hip flexors, gluteus musculature, quadriceps, and gastrocnemius-soleus complex. These exercises will include (but are not limited to) leg lifts, hip abductions, and calf presses.

The participants will be instructed to perform the upper and lower body exercises prescribed for a duration of 30 minutes 3 times per week. Participants will perform 1-3 sets of 12 repetitions of each exercise. Most of the exercises will require the use of exercise bands. Once they are able to perform 3 sets of 12 repetitions of an exercise, they will graduate to the next level of increasing resistance. The participants will be given a set of three bands which determine the level of resistance: easy, moderate, and hard. They will record the date, the color of elastic exercise band used, the number of repetitions and sets, and their perceived intensity of the exercise based on the Borg Rating of Perceived Exertion (RPE) scale (the scale will be included in the participants' activity log).

The participants in the strengthening program will be encouraged to complete an additional 5 minutes of stretching daily. They will be provided with a handout demonstrating upper and lower body stretches to help alleviate the onset of delayed muscle soreness.

All participants will be encouraged to perform stretches before and after their strengthening exercises. We will provide them with diagrams of sample stretches they may perform.

#### b) Walking program

All participants will be instructed to initiate a walking program. The walking program will consist of walking at a comfortable pace for 20 to 30 minutes during each walking session. They will walk at least three times a week. The goal is to achieve a fairly light intensity of exercise (Borg RPE of 8-10) and progress a moderate intensity (Borg RPE of 11-12). Each participant will be provided a pedometer and will be instructed to record the number of steps taken each day.

Each participant will meet face-to-face with a member of the research staff. The participant will receive a patient exercise booklet that includes information on exercise, research staff contact info, exercise precautions, diagrams on the exercises, and the exercise and activity log. They will also receive a pedometer and exercise bands. Each participant will watch the exercise video clips on a computer or have the exercises demonstrated to them. The patient will have the opportunity to perform the exercise or request for the exercise to be demonstrated again for them. Thus, every participant receives the same education on the exercise regimen. We can also email them a link for the exercise clips to review from home. Furthermore, they will be instructed on the use of the pedometer and for filling out their exercise logs during the initial visit.

Each participant will be issued an exercise activity log book to record their daily activity: record their walking activity (time, intensity, number of steps) and to record the number of exercises they are able to complete during each exercise session (time, intensity, types of exercises, repetitions). They will also include if they performed exercises or activities not outlined in our study.

These activity log books will be used to monitor the patients' activity adherence.

If participants have internet access and choose to enter their exercise activity online, they will be asked to use the Redcap system to log their exercise activity on a daily basis. With their consent, participants will receive daily email reminders with a Redcap program link to log their aerobic and resistance exercise activity, pedometer steps, and to report any barriers or difficulties with their exercises. Participants will still have the option to complete activity logs on paper and the resistance exercise log of individual exercises will still remain on paper.

REDCap is a mature, secure web application for building and managing surveys and databases. While REDCap can be used to collect virtually any type of data, it is specifically geared to support data capture for research studies. REDCap can accommodate complex relationships among tables, allowing large quantities of data to be integrated into a single database. Relational databases such as REDCap also allow for powerful and flexible queries and reports. These features include more user-friendly interfaces, the ability to specify valid ranges for variables, and double-entry systems for data, all of which help to maintain data integrity. REDCap provides audit trails for tracking data manipulation and user activity, as well as automated export procedures for seamless data downloads to Excel, PDF, and common statistical packages (SPSS, SAS, Stata, R). We will use the built-in security features of REDCap to restrict user access.

Furthermore, to monitor for adherence and to screen for any exercise intolerance or exercise barriers, the participants will be counseled face-to-face by our research assistant during their follow up visits regarding their progress of their exercise program. The research assistant will be provided with a list of screening questions to address exercise adherence and to assess for advancing the participant's strengthening program. The research assistant will also implement behavior interventions to encourage continued adherence to the exercise program, which will include education on the benefits of exercise and physical activity. There will be one telephone follow up during week 6 of enrollment to ensure the participants do not have questions about their exercise program. They will receive a reminder to wear the pedometer and to complete the daily exercise logs.

The packet includes a list of exercise precautions and also advises the patients to not use their exercise resistance bands when their platelet counts are less than 20 K/ul.

The participants will also be given the telephone contact information of the research staff in case they encounter problems during the exercise intervention period. In the

event of an acute musculoskeletal injury or cardiopulmonary distress, the patient will be managed with an appropriate medical referral. Participants in the outpatient group who are admitted to the hospital for an acute medical concern will also be followed. They will need clearance from their HSCT physician and/or physical medicine and rehabilitation physician to continue with their exercise intervention. They will be encouraged to continue with their exercise program (and record their activity) if their medical condition allows for it. Furthermore, patients who develop significant functional decline that requires supervision and management from a skilled therapist will be referred to inpatient and/or outpatient physical and occupational therapy when appropriate.

As current standard-of-care, some of the patients who are seen in the ambulatory treatment center (ATC) are referred to outpatient physical therapy for an exercise program. These are usually group sessions for patients who do not required one-on-one treatment sessions with a physical therapist. If a participant in our study is enrolled in this outpatient ATC physical therapy program, they will still utilize our exercise program on their non-therapy days and in some situations, they may perform our exercises (aerobic and/or resistance regimens) during their therapy session to fulfill their exercise requirement for the day. Again, the participant will complete their daily log so we may track how much exercise they are performing each day.

If the patient falls or has an adverse event, they are instructed to call their stem cell transplant physician. These patients receive extensive counseling after their stem cell transplant on when and how to contact their stem cell transplant physician and team. If there are questions and concerns about the exercise regimen or intolerance of certain exercises, the participant should call our research staff directly. The Physical Medicine and Rehabilitation physicians will be communicating directly with research team on a weekly basis to discuss any adverse events or concerns.

It is anticipated that a fully adherent participant would be able to complete 30 minutes of exercise daily, five times per week, which equates to approximately 150 minutes of exercise per week.

Equipment provided:

- Notebook for the exercise activity log (\$10-20 each x 40)
- Pedometer: EKHO One Pedometer http://www.amazon.com/Ekho-1277210-EKHO-One- Pedometer/dp/B002MACRUC/ref=sr\_1\_2?ie=UTF8&qid=1449008114&sr=8- 2&keywords=ekho+one+pedometer
- Resistance exercise bands: therabands in 3 different levels of resistance http://www.amazon.com/Thera-Band-Latex-Exercise-Bands- YELLOW/dp/B00SX165ZC/ref=pd\_sim\_328\_1?ie=UTF8&dpID=415g8eKmdtL&d pSrc=sims&preST=\_AC\_UL160\_SR160%2C160\_&refRID=1HQKCG0DCF55KP ZRVKRC

Equipment needed:

- Handheld dynamometer: microFET 2 Hoggan Health Industries (\$1095)
   http://www.hogganhealth.net/microfet2.php
- Stop watch

The participants will not receive monetary compensation for their participation in this study as this is an unfunded pilot study. The patients are not returning for any follow-up visits as they will be seen during their normally scheduled clinic visit. There would be no burden of extra return visits specifically for the study. However, the participants' benefit and incentive for participating in this study is they will receive exercise education and an exercise regimen, which will be beneficial in these newly-diagnosed GVHD patients.

# **VI. STATISTICS:**

The objective of this study is to estimate change in the six functional/physical measures (described in Section VI) over time. The information gained in this study will be used for future larger studies. These measures will be collected at baseline, two weeks, 4 weeks, and 8 weeks. Other secondary endpoints, such as patients' Self Reported Improved (or PROMIS) Health Assessment Questionnaire, PROMIS Short Form v1.0 – Physical Function 12a, MDASI, FACT-Fatigue, GVHD associated measures and corticosteroid dose will also be collected over the same time course. We plan to approach 70 patients (3 patients each month for an approximate period of 24 months of accrual). We expect that about 85% (60 patients) will agree to participate in the study. Further if 10 (20%) out of 60 patients drop out early due to developing significant weakness, disease progression, or have a prolonged and complicated inpatient hospital course, we expect 50 patients to complete the 8 week measures. With 50 patients, we will have an 80% power to detect an effect size of 0.404 in a functional measure change from baseline to 8 weeks using a paired t-test with a 0.05 two-sided significance level.

To explore the possible corticosteroid dose effect on the functional measures, graphical methods will be used to present data and the cumulative steroid exposure may be correlated with functional measures over time in a repeated measures analysis when appropriate. Furthermore, 2-week or 4-week cumulative steroid exposure may be compared between 6-month non-relapse deaths and others, provided patients all survive past 2 weeks or 4 weeks.

We expect about 20% non-relapse mortality rate at 6 months (NRM6). With about 10 non-relapse deaths, we will explore potential difference in baseline and/or the change of functional/physical measures between 6-month non-relapse deaths vs others. With 10 non-relapse deaths and 40 others, we will have an 80% power to detect an effect size of 1.011 in the difference of a functional measure at baseline between two groups using a two-sample t-test with a 0.05 two-sided significance level.

We will also evaluate adherence rates to the exercise regimen and drop-out rates/patterns, which is very important for the future larger study planning.

At the end of the study, we will summarize the pattern of the functional/physical measure change, pattern of exercise and other secondary measures, using collected information from all 50 patients. Repeated measures analysis or generalized estimating equation maybe applied to estimate the magnitude of the measure change over time. In the same model we will also evaluate the correlation between/among different measures. These models incorporate the intra-patient correlation into consideration when these measures are recorded multiple times from each patient.

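### Does labelling 10 early dropouts out of 60 as 20% undermine the planned sample or its power?

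*Combined protocol and SAP*

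**What the plan says.** Section VI (Statistics) builds its numbers in four steps.

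- **Approached:** "We plan to approach 70 patients (3 patients each month for an approximate period of 24 months of accrual").
- **Enrolled:** "We expect that about 85% (60 patients) will agree to participate in the study".
- **Early dropout:** "Further if 10 (20%) out of 60 patients drop out early", for reasons such as marked weakness, disease progression or a complicated hospital stay.
- **Completers:** "we expect 50 patients to complete the 8 week measures".

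The primary power statement then uses the completer count: "With 50 patients, we will have an 80% power to detect an effect size of 0.404" for the change from baseline to 8 weeks, "using a paired t-test with a 0.05 two-sided significance level". Later in the section a comparison by 6-month non-relapse mortality is sized as "With 10 non-relapse deaths and 40 others, we will have an 80% power to detect an effect size of 1.011", and the closing paragraph describes a final summary "using collected information from all 50 patients".

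**The concern.** The dropout clause names its own numerator and denominator, and they do not give the percentage printed between them. Rounding does not explain the gap, since 16.7% rounds to 17%. The preceding step, about 85% for 60 of 70, does round acceptably, so the reader has no reason to expect loose percentages here.

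The clause sits at the point where 60 enrolled patients become the 50 behind the power statement. If the percentage were the real assumption and the count the error, the completers would be 48 and the stated power would rest on two patients too many. A reader who sees 20% could also suspect the familiar mistake of inflating 50 by 20% to reach 60, where division by 0.80 is required. In a study meant to inform later and larger ones, a wrong dropout figure could be carried forward.

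**Working it through.** **Inputs**, all from Section VI: 70 approached; about 85% (60) agreeing; 10 early dropouts, labelled 20%; 50 completers; effect size 0.404 with 80% power; paired t-test, two-sided 0.05.

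**1. Agreement step.** 0.85 × 70 = 59.5 and 60/70 = 85.7%. Consistent with the stated approximate 85%.

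**2. Dropout step.**
- 10/60 = 16.7%, so the label does not reproduce.
- 0.20 × 60 = 12, which would leave 60 − 12 = 48.
- 10/50 = 20%, so the label fits dropouts over completers.
- 50 × 1.20 = 60 also fits, as an incorrect inflation. The correct one at 20% is 50/0.80 = 62.5, that is 63 enrolled; at one in six it is 50/(1 − 1/6) = 60.

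The documents do not say how the 20% arose, so either origin is a guess. The counts are consistent among themselves: 60 − 10 = 50.

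**3. Primary power statement.** Power = P(|T| > t(0.975, n − 1)), where T is noncentral t with n − 1 degrees of freedom and noncentrality d√n.

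| Completers | Noncentrality at d = 0.404 | Power at 0.404 | Effect detectable with 80% power |
|---|---|---|---|
| 50 (as planned) | 0.404 × √50 = 2.857 | 79.96% | 0.4042 |
| 48 (if 20% were meant) | 0.404 × √48 = 2.799 | 78.3% | 0.4129 |

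The plan's 0.404 reproduces at n = 50 and not at n = 48, so it was computed from the count and not from the percentage. The difference between the rows is 1.7 percentage points of power, or 0.4129 − 0.4042 = 0.009 in effect size.

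**4. The mortality comparison.** For 10 against 40, the noncentrality at 1.011 is 1.011 × √(10 × 40/50) = 2.860. Two-sided power is 80.0% and the detectable effect 1.0109, so that figure also recomputes. It is not independent evidence for 50 completers. The comparison concerns a measure at baseline, which every enrolled patient should have, grouped by death up to Day 180. Applying the stated 20% mortality to all 60 would give 12 against 48 and a detectable effect of about 0.92. The split shows only that the authors carried 50 forward; whether it is the best denominator there is a separate matter, not settled here.

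**The case for a change.** The best argument for a correction is that this is the only dropout rate the plan states, and that Section VI itself stresses the value of dropout information for planning a larger study. Observed dropout may be compared with this assumption, and 20% and 16.7% are different benchmarks. A planner who took the 20% and wanted 50 completers would enrol 63, not 60. Correcting one percentage costs almost nothing.

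Part of this stands: the figure is wrong, nothing elsewhere in the document corrects it, and no extraction fault explains it. The argument for consequence does not. The sentence prints 10, 60 and 50 alongside the percentage, so anyone using it can see the slip and recover the intended numbers. The figure is introduced by a conditional, as a planning supposition; it is not a threshold, a stopping criterion or an analysis parameter. A later study would be planned from the dropout this pilot observes, not from what it supposed beforehand. Three more patients in that later study would be a small effect even if someone did use the label.

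**Conclusion.** The percentage is a clerical slip: it should read about 17%. It calls for no change to the plan. The path from 60 enrolled to 50 completers is arithmetically sound, and the 0.404 effect size at 80% power follows from 50 patients.

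This conclusion assumes that the counts, and not the percentage, express the intention. The support is that 60 − 10 = 50 closes within the sentence and that 0.404 reproduces only from 50. If the sponsor had meant 20%, there would be 12 dropouts, 48 completers, 78.3% power at 0.404 and a detectable effect of 0.413. For an unfunded pilot intended to estimate change over time, that alternative would not alter the design, the analysis or the reading of the results. No judgement is made here on the 10 against 40 mortality split beyond noting that its stated figure recomputes.
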